7.2 Serious adverse event reporting

To ensure subject safety, every SAE, regardless of causality, occurring from after the subject has provided informed consent and until 3 months after his/her last dose of CFZ533 or 2 months after the EoS visit for patients on SoC treatment must be reported to Novartis within 24 hours of learning of its occurrence.

A SAE form for each confirmed acute rejection event should be completed since these are considered to be “medically significant events” for this clinical trial requiring timely and detailed reporting. The SAE form should be completed as soon as the PI at the site confirms the event based on the histological report from the local pathologist together with a clinical assessment of the event.

Recurrent episodes, complications, or progression of the initial SAE must be reported as follow-up to the original episode, regardless of when the event occurs. This report must be submitted within 24 hours of the Investigator receiving the follow-up information. An SAE that is considered completely unrelated to a previously reported one should be reported separately as a new event.

Information about all SAEs (*either initial or follow up information*) is collected and recorded on the paper Serious Adverse Event Report Form. The Investigator must assess the relationship to *each specific component of study treatment (if study treatment consists of several drugs)* complete the SAE Report Form in English, and send the completed, signed form by fax within 24 hours after awareness of the SAE to the local Novartis Drug Safety and Epidemiology Department. The telephone and fax number of the contact persons in the local department of Drug Safety and Epidemiology, specific to the site, are listed in the Investigator folder provided to each site. The original copy of the SAE Report Form and the fax confirmation sheet must be kept with the case report form documentation at the study site. Follow-up information should be provided using a new paper SAE Report Form stating that this is a follow-up to a previously reported SAE.

Follow-up information provided should describe whether the event has resolved or continues, if and how it was treated, whether the treatment code was broken or not and whether the subject continued or withdrew from study participation. Each re-occurrence, complication, or progression of the original event should be reported as a follow-up to that event regardless of when it occurs.

If the SAE is not previously documented in the Investigator's Brochure or Package Insert (new occurrence) and is thought to be related to the investigational treatment, a Drug Safety and Epidemiology Department associate may urgently require further information from the Investigator for Health Authority reporting. Novartis may need to issue an Investigator Notification (IN) to inform all Investigators involved in any study with the same investigational treatment that this SAE has been reported. Suspected Unexpected Serious Adverse Reactions (SUSARs) will be collected and reported to the competent authorities and relevant ethics committees in accordance with EU Guidance 2011/C 172/01 or as per national regulatory requirements in participating countries.

7.3 Pregnancy reporting

To ensure patient safety, each pregnancy occurring while the patient is on study treatment must be reported to Novartis within 24 hours of learning of its occurrence. The pregnancy should be followed up to determine outcome, including spontaneous or voluntary termination, details of the birth, and the presence or absence of any birth defects, congenital abnormalities, or maternal and/or newborn complications.

Pregnancy should be recorded on a Clinical Trial Pregnancy Form and reported by the Investigator to the local Novartis Drug Safety and Epidemiology Department. Pregnancy follow-up should be recorded on the same form and should include an assessment of the possible relationship to the investigational treatment to pregnancy outcome. Any SAE experienced during pregnancy must be reported on the SAE Report Form.

Any SAE experienced during pregnancy must be reported on the SAE Report Form. If a patient of a US study center becomes pregnant, please also refer to the country-specific instructions in [Appendix 2](#).

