(6) First dose of CFZ533 will be administered intravenously pre- or intra-operatively and must be completed by the time of unclamping or up to 6 hours prior to the time of unclamping. Other study drugs (e.g., Tac, MMF, CS) should be started within 24 hours post-transplantation or according to local practice.

(7) First dose of basiliximab induction should be given within 2 hours prior to transplant surgery, or according to local practice. The second dose should be given on Day 4, or according to local practice.

(8) Local laboratory tests include: hematology, urinalysis, serum chemistries, renal function, and coagulation parameters.

(9) Obtained every 15 mins for 2 hrs after the start of the first CFZ533 IV infusion or time of SC injection.

(10) Negative test result must be available prior to randomization/enrollment.

(11) Blood collections and safety assessments should be taken pre-dose if the sampling falls on a dosing day.

(12) Blood draws for trough concentrations should be performed before the next dose is given. In addition, they should be performed locally as shown and additionally 5±2 days following each clinic visit in which doses are changed.

Corporate Confidential Information

(14) All serious adverse events, serious infections and pregnancies must be reported from informed consent until 3 months after his/her last dose of CFZ533 or 2 months

after EoS visit for patients on SoC treatment.

- (15) Induction therapy (e.g., basiliximab) and pre-transplant immunosuppression (if used) should be recorded on the Concomitant Medications CRF page under the Immunosuppressive category.
- (16) Prophylaxis for CMV, PCP, HBV, BK and oral candida to be considered per protocol [Section 5.5.8](#), and recorded on the Concomitant Medications CRF page if administered.
- (17) All patients are expected to continue in the study to Month 6 or 12 and complete the Month 6 or 12 Completion page, regardless of whether they are on or off study medication. If subjects discontinue study treatment, he/she should continue in the study on SOC per local practice and attend study visits to Month 6 or 12. Any permanent discontinuation of the randomized study regimen should be recorded on the appropriate DAR CRF pages. After discontinuation of study regimen, the immunosuppressive regimen prescribed should be recorded on the Concomitant Medications CRF under the Immunosuppressive category.

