4.2 Exclusion criteria

Subjects fulfilling **any** of the following criteria are not eligible for inclusion in this study:

1. Use of other investigational drugs at the time of enrollment, or within 30 days or 5 half-lives of enrollment, whichever is longer.
2. History of hypersensitivity to any of the study drugs or to drugs of similar chemical classes.
Corporate Confidential Information
4. Recipients of an organ from a non-heart beating donor.
5. ABO incompatible or complement-dependent lymphocytotoxic (CDC) crossmatch positive transplant (isolated positive B cell crossmatches are not an exclusion criterion).
6. Subjects receiving a second kidney allograft, unless the first allograft was lost due to surgical complication.
7. Subjects at high immunological risk for rejection as determined by local practice for assessment of anti-donor reactivity (e.g., high PRA $>$ 20%, presence of pre-existing

Corporate Confidential Information

10. Subjects at risk for tuberculosis (TB), specifically subjects who:
 - Have current clinical, radiographic or laboratory evidence of active or latent TB
 - Have a history of active TB
 - a. Within the last 2 years even if it was treated
 - b. Greater than 2 years ago, unless there is documentation of adequate treatment according to locally-accepted clinical practice
 - In the opinion of the Investigator and based upon an appropriate evaluation, have a

Corporate Confidential Information

13. Subject with severe systemic infections, current or within the two weeks prior to randomization/enrollment.

16. History of malignancy of any organ system (other than localized basal cell carcinoma of the skin), treated or untreated, within the past 5 years, regardless of whether there is evidence of local recurrence or metastases.

Corporate Confidential Information

18. Pregnant or nursing (lactating) women, where pregnancy is defined as the state of a female after conception and until the termination of gestation, confirmed by a positive hCG laboratory test.

19. Women of child-bearing potential, defined as all women physiologically capable of becoming pregnant, unless they are using highly effective methods of contraception during dosing and for 12 weeks after the study medications have been stopped. Highly effective contraception methods include:

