5.5.10 Discontinuation of study treatment and premature subject withdrawal

Study “Stopping rules”

The following stopping rules based on potential toxicities will serve as the basis for placing the study on hold. Although the stopping criteria do not incorporate an absolute requirement for causality, the potential relationship between an AE and CFZ533 will be evaluated carefully on a case-by-case basis between the Sponsor and the Investigator. Following a review of the AE(s), a decision to permanently discontinue enrollment or re-initiate dosing will be made by the DMC.

- Two (2) or more patients presenting with PTLD or PML

In addition, specific stopping rules for the incidence of tBPAR will be applied. These rules are designed to ensure that a CFZ533 treatment arm will be stopped if there is high probability (>90%) that the true tBPAR rate is greater than 20%. Corporate Confidential Information

Corporate Confidential Information

In addition to the automatic hold criteria and tBPAR criteria presented above, the DMC will review safety data regularly as outlined in their charter (see [Section 8.4](#)) during quarterly and *ad hoc* meetings. The DMC can recommend stopping a specific study arm(s) or the entire trial if significant changes or effects that, in their collective opinion, are deemed unsafe or unethical to continue administering CFZ533.

Discontinuation of study regimen

The Dosage Administration Records for CFZ533 (all parts), MMF and Tac (Part 1 only) and Concomitant Medication eCRF for MMF and Tac (Part 2) will be used to record if a subject has permanently discontinued study treatment and why.

Possible reasons for study treatment discontinuation are:

- Adverse Event
- Lack of Efficacy
- Technical problem during transplant surgery
- Subject/Guardian Decision
- Lost to follow-up
- Death
- Graft Loss

The Investigator should discontinue a subject from their randomized treatment regimen if, on balance, he/she believes that continuation would be detrimental to the subject's well-being.

Subjects who become pregnant while taking study medication must be discontinued from study medication and from the study, such pregnancies should be reported as SAEs to Novartis DSE and entered as AEs in the eCRF, the reason for discontinuation of study medication should be recorded as AE and reason for discontinuation from study is pregnancy (see next section below).

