Subjects who discontinue study medication (CFZ533 or Tac) should remain in the study, if possible, and receive standard of care immunosuppression, according to local practice, until completing the study at Month 6 (Part 1) or Month 12 (Part 2). Visits and assessments for such subjects are described in the [Assessment schedule](#). All immunosuppressants after discontinuation of study regimen must be recorded on the Concomitant Medication eCRF under the Immunosuppressive category.

Subjects who discontinue their study treatment regimen should NOT be considered withdrawn from the study UNLESS they withdraw their consent to participating in all the elements of the study (see [Section 5.5.11](#)). Information on treatment discontinuation needs to be captured on the end of treatment eCRF page. Such subjects should remain in the study, if possible, and receive standard of care immunosuppression, according to local practice, until completing the study at Month 6 (Part 1) or Month 12 (Part 2). See the [Assessment schedule](#) for the required assessments of these subjects after discontinuation of study regimen. If they fail to return for these assessments for unknown reasons, every effort should be made to contact them as specified in [Section 5.5.12](#).

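### Protocol Section 7.3 gives a narrower pregnancy-reporting window than schedule footnote 14, and Section 5.5.10 takes pregnant subjects out of a follow-up that the protocol otherwise keeps for everyone off treatment

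*Protocol*

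**What the plan says.** **Reporting window.** Protocol Section 7.3 requires that "each pregnancy occurring while the patient is on study treatment must be reported to Novartis within 24 hours" of the site learning of it. It then asks for follow-up of the pregnancy to its outcome. It gives no period after treatment and does not define when a patient ceases to be on study treatment.

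Footnote 14 of the assessment schedule is wider: "All serious adverse events, serious infections and pregnancies must be reported from informed consent until 3 months after his/her last dose of CFZ533", or for two months "after EoS visit for patients on SoC treatment". Section 7.2 sets the same limits for serious adverse events: "until 3 months after his/her last dose of CFZ533 or 2 months after the EoS visit for patients on SoC treatment". Exclusion criterion 19 in Section 4.2 requires contraception "during dosing and for 12 weeks after the study medications have been stopped".

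**Study status.** Section 5.5.10 says that a subject who becomes pregnant while taking study medication "must be discontinued from study medication and from the study". The same sentence makes the pregnancy reportable as a serious adverse event and tells the site to record pregnancy as why she left the study. Further on, the same section says that subjects who stop their study regimen "should NOT be considered withdrawn from the study UNLESS they withdraw their consent" to all elements of the study. Section 3.1.2, Section 6 and schedule footnote 17 also expect subjects to stay to Month 6 (Part 1) or Month 12 (Part 2), on or off treatment.

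**The concern.** Section 7.3 is the section headed as the pregnancy-reporting rule, yet its wording is narrower than a footnote to the visit schedule. A conception shortly after the last CFZ533 dose falls inside the footnote's window but may fall outside Section 7.3. The serious-adverse-event route does not clearly close the gap: Section 5.5.10 makes a pregnancy reportable by that route only when it begins while the subject is taking study medication, and pregnancy is not itself among the seriousness criteria in Section 7.1. This is a first-in-transplant antibody given with mycophenolate, for which the protocol describes fetal risk, so each such pregnancy matters individually.

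The second conflict concerns follow-up. A woman who leaves the study because she is pregnant no longer attends the visits at which graft and survival status are recorded, whereas a subject who stops treatment for almost any other reason does.

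**Working it through.** The documents give no figure to reproduce. The check compares the windows and does day arithmetic for a Part 2 patient who completes CFZ533 dosing.

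**Inputs**
- Last planned CFZ533 dose, Part 2: about Day 337 (Section 3.1.4).
- Study Completion visit, Part 2: Day 364 (Appendix 1).
- Study Month: 28 days (schedule legend; Section 3.1.2).
- Dosing interval added when treatment duration is calculated: 28 days (Section 9.3.1).
- Three calendar months: taken as 91 days, an assumption, because footnote 14 does not say which kind of month it means.

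**End of the footnote 14 window**
- Study months: 337 + 3 × 28 = Day 421.
- Calendar months: 337 + 91 = Day 428.

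**Gap left by Section 7.3, by reading of on study treatment**

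| Treatment taken to end at | Gap, 28-day months | Gap, calendar months |
|---|---|---|
| Last CFZ533 dose (Day 337) | 421 − 337 = 84 days | 428 − 337 = 91 days |
| One dosing interval later (337 + 28 = Day 365) | 421 − 365 = 56 days | 428 − 365 = 63 days |
| End of background therapy | smaller; cannot be fixed from the text | smaller; cannot be fixed from the text |

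The footnote window runs 421 − 364 = 57 to 428 − 364 = 64 days past the completion visit, so most of it lies after the last scheduled contact in clinic. The contraception period is 12 × 7 = 84 days, close to the footnote window. For control patients the footnote adds two months after the end-of-study visit, 2 × 28 = 56 days in study months.

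In Part 1 the last CFZ533 dose is on Day 71, and 71 + 84 = Day 155, the completion visit. The Part 1 blood log has a pregnancy sample on that day. The Part 2 log has one at Day 364, 364 − 337 = 27 days after the last dose. The protocol therefore tests for pregnancy at times after the last dose.

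**What leaving the study removes**

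| Item | Effect if a pregnant subject leaves the study |
|---|---|
| Pregnancy report and outcome | Kept: Sections 5.5.10 and 7.3 require both |
| Month 3 tBPAR, primary analysis | Little effect: only on-treatment events count (Section 9.4.2) |
| Month 6 and 12 tBPAR, supportive | Little effect: same method (Section 9.4.3) |
| eGFR | Little effect: values after stopping randomized treatment are missing or excluded (Protocol 9.5.3.1, SAP 7.1.2) |
| Kaplan-Meier tBPAR | Her time is cut at last contact (SAP 6.1.4) |
| Graft loss and death at Months 6 and 12 | Scheduled collection lost (Section 9.5.1) |
| Safety data after stopping treatment | Lost, although Section 9.5.3 analyses them |

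**Number at risk.** Planned CFZ533-treated patients: 30 (Arm 2A) + 6 (Arm 1) = 36. The documents do not say how many will be women of child-bearing potential.

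**The case against.** The strongest reply is that footnote 14 is already mandatory. Section 7.3 does not exempt later pregnancies, so a site can comply with both texts, and Section 6 requires safety contact for three months after the last CFZ533 dose. Appendix 2 adds US registry reporting for conceptions within six weeks of stopping mycophenolate. All this is correct. The gap arises only where a site follows Section 7.3 alone, but that is a plausible error.

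A reader might infer that Section 7.3 ends reporting at the last dose, leaving no days against about 90. The text does not say so. The glossary includes background therapy in study treatment, and Section 5.5.15 lets mycophenolate continue unchanged after CFZ533. Against that, the glossary also counts permanently stopping any one component as study drug discontinuation. The end point is undefined, and 84 to 91 days is the upper end of a range.

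A reader might also infer that removal from the study loses the exposed pregnancy, or takes the woman's rejection and graft outcome out of the Month 12 comparison. Neither holds as stated. The pregnancy remains reportable and is followed to outcome. Section 7.3 also requires any serious adverse event during pregnancy to be reported, and confirmed acute rejection and graft loss are such events (Sections 7.2 and 6.5.1). The tBPAR and eGFR analyses are on-treatment, and she stops study medication in any case.

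Finally, the removal in Section 5.5.10 may be a deliberate exception, since its sentence also names the reason to record. That is possible, but the protocol gives no rationale, and the general rule admits only withdrawal of consent.

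**Conclusion.** Both inconsistencies are real and minor. Section 7.3 and footnote 14 give different reporting windows. For a Part 2 CFZ533 completer the difference is 84 to 91 days or 56 to 63 days on the two CFZ533-based readings, and less if background therapy counts. This rests on a last dose near Day 337 and on whether a month means 28 days or a calendar month. A pregnancy goes unreported only if a site relies on Section 7.3 without the footnote.

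Section 5.5.10 conflicts with the follow-up rule stated in that section, in Sections 3.1.2 and 6, and in footnote 17. The loss is mainly scheduled Month 6 and Month 12 graft loss and death, together with safety data after stopping treatment, for very few women. The primary result is not threatened. The case for acting rests on safety capture and internal consistency.

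**What to change.** 1. In Section 7.3, replace the on-treatment condition with the window already in footnote 14: from informed consent until three months after the last CFZ533 dose, or two months after the end-of-study visit for standard-of-care patients.
2. Reconcile the pregnancy sentence in Section 5.5.10 with the follow-up rule in the same section, Section 3.1.2 and footnote 17, so that follow-up data can still be collected with the subject's consent. Two places in that sentence need amending: the words that take her out of the study, and the later clause that records pregnancy as the reason for leaving it. Changing only one would create a new contradiction. The rule on stopping study medication stays as it is.

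The cost is a few wording changes at the next amendment. No new analysis is needed, and any continued follow-up would use the visits already scheduled for subjects off treatment.

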7.4 Early phase safety monitoring

The Investigator will monitor AEs in an ongoing manner and inform the Sponsor of any clinically relevant observations. Any required safety reviews will be made jointly between medically qualified personnel representing the Sponsor and Investigator. Such evaluations may occur verbally, but the outcome and key discussion points will be summarized in writing (e-mail) and made available to both Sponsor and all Investigator(s). Criteria pertaining to stopping the study/treatment or adapting the study design are presented above.

When two or more clinical site(s) are participating in the clinical study, the Sponsor will advise the Investigator(s) at all sites in writing (e-mail) (and by telephone if possible) of any new, clinically relevant safety information reported from another site during the conduct of the study in a timely manner.

8 Data review and database management

8.1 Site monitoring

Before study initiation, at a site initiation visit or at an Investigator's meeting, a Novartis representative will review the protocol and eCRFs with the Investigators and their staff. During the study, the field monitor will visit the site regularly to check the completeness of patient records, the accuracy of entries on the eCRFs, the adherence to the protocol and to Good Clinical Practice, the progress of enrollment, and to ensure that study drug is being stored, dispensed, and accounted for according to specifications. Key study personnel must be available to assist the field monitor during these visits.

The Investigator must maintain source documents for each subject in the study, consisting of case and visit notes (hospital or clinic medical records) containing demographic and medical information, laboratory data, electrocardiograms, and the results of any other tests or assessments. All information on eCRFs must be traceable to these source documents in the subject's file. The Investigator must also keep the original informed consent form signed by the subject (a signed copy is given to the subject).

The Investigator must give the monitor access to all relevant source documents to confirm their consistency with the eCRF entries. Novartis monitoring standards require full verification for the presence of informed consent, adherence to the inclusion/exclusion criteria, documentation of SAEs, and the recording of data that will be used for all primary and safety variables. Additional checks of the consistency of the source data with the eCRFs are performed according to the study-specific monitoring plan. No information in source documents about the identity of the subjects will be disclosed.

